5 STUDY DRUGS, ADMINISTRATION AND DURATION

The protocol-specified ARV regimens are:

- Whole Tablet Period: Single observed oral dose of Genvoya whole tablet (EVG 150mg/COBI 150mg/FTC 200mg/TAF 10mg) under direct observation.
- Crushed/Dissolved Tablet Period: Single observed oral dose of Genvoya crushed/dissolved tablet (EVG 150mg/COBI 150mg/FTC 200mg/TAF 10mg) under direct observation.

Genvoya will be administered with a light meal. Crushed/dissolved Genvoya tablet solution will be

prepared at the Johns Hopkins Investigational Pharmacy.

Genvoya tablets will be donated by Gilead Sciences and will be dispensed by the Johns Hopkins Investigational Pharmacy. The Johns Hopkins Investigational Pharmacy will also maintain complete records of all study medications. All unused study medications must be returned to the Johns Hopkins Investigational Pharmacy after the study is completed or terminated. Unused or returned study medications will be destroyed.

6 STUDY POPULATION

Up to twenty male and female health research participants will be enrolled in this study to assure twelve individuals complete the trial. All participants will meet inclusion/exclusion criteria as outlined in this protocol. Healthy research participants will be recruited by the Johns Hopkins DDU staff.

7 SELECTION AND ENROLLMENT OF STUDY PARTICIPANTS

7.1 Inclusion Criteria

- 7.1.1 Healthy adults ≥ 18 years of age.
- 7.1.2 Negative HIV-1/2 Ag/Ab serology documented within 30 days prior to study entry.
- 7.1.3 Negative Hepatitis B surface antigen within 30 days prior to study entry.
- 7.1.4 Ability and willingness of subject to provide a signed informed consent and comply with study requirements.
- 7.1.5 Negative POCT qualitative urine pregnancy test (female participants only).
- 7.1.6 All subjects must not participate purposely in a conception process (e.g., active attempt to impregnate, sperm donation, or in vitro fertilization). If participating in sexual activity that could lead to pregnancy subjects must take every precaution to avoid risk of pregnancy by using a reliable contraception for the duration of the study therapy (e.g., condoms, hormonal, barrier).
- 7.1.7 Laboratory values and physical examination as judged by the principal investigator to be safe to participate including normal renal function.
- 7.1.8 Good peripheral venous access for proposed pharmacokinetic sampling.
- 7.1.9 Willingness and ability to take oral medications.

7.2 Exclusion Criteria

- 7.2.1 History of chronic or acute medical conditions that in the opinion of the investigator would jeopardize safety of subjects participating in this study.
- 7.2.2 Known or suspected hypersensitivity to the components of Genvoya.
- 7.2.3 Currently taking or having taken oral PrEP or PEP (e.g. Truvada[®]) within 30 days of study entry, or anticipated use of PrEP/PEP during study participation
- 7.2.4 Use of prescription or over-the-counter medications, including agents containing polyvalent cations (e.g., Mg, Al, Fe, or Ca), or any other drugs that in the opinion of the investigator could interfere with the pharmacokinetics of any of the ARV components of Genvoya within 2 weeks prior to either study dose.
- 7.2.5 Pregnant or breast feeding.

- 7.2.6 Active drug or alcohol use or dependence that, in the opinion of the investigator, would interfere with adherence to study requirements.
- 7.2.7 Hospitalization or therapy for serious illness within 30 days prior to study entry as judged by the investigator.
- 7.2.8 Participation in any investigational drug study within 30 days prior to study entry that in the opinion of the investigator would preclude study participation.
- 7.2.9 Taking any medication listed in the package insert that is contraindicated with Genvoya.
- 7.2.10 Any other condition or prior therapy that, in the opinion of the investigator, would preclude informed consent, make study participation unsafe, make the individual unsuitable for the study or unable to comply with the study requirements. Such conditions may include, but are not limited to, current or recent history of severe, progressive, or uncontrolled substance abuse, or renal, hepatic, hematological, gastrointestinal, endocrine, pulmonary, neurological, or cerebral disease.

8 CONCOMITANT AND PROHIBITED MEDICATIONS

Use of any licensed drugs during the study is prohibited unless medically required for the safety of the subjects, and requires prior approval by the study investigators. If a concomitant medication is needed and approved by the study investigators, the package insert will be reviewed to ensure that the team has the most current information on drug interactions. Concomitant use of herbals, dietary supplements, nutritional supplements, or any other complementary and alternative medicine compounds containing polyvalent cations (e.g., Mg, Al, Fe, or Ca) is not allowed from the 14 days prior to, and 3 days following each study dose. Investigational medications are also prohibited.

9 CLINICAL AND LABORATORY EVALUATIONS

Study Schedule

The study visits are described below as to their timing, procedures, and sample collections and summarized in **Table 3** Schedule of Events.

9.2 Definitions for Study Schedule

9.2.1 Screening (Visit 1)

Screening will be scheduled at the Johns Hopkins DDU and must occur prior to the subject taking any study medication. At the beginning of the screening visit, subjects will be asked to read and sign the informed consent approved by the Johns Hopkins IRB, and will undergo screening laboratory and clinical evaluation. Eligibility of study participation will be determined by screening evaluations. Screening evaluations to determine eligibility must be completed within 30 days prior to study entry and administration of study drugs.

The following assessment and procedures will be performed at screening visit:

- Medical/Medications history
- Physical examination (including vital signs, weight and height)

- HIV-1/2 Ag/Ab serology and Hepatitis B surface antigen testing
- POCT qualitative urine pregnancy test (female participants only)
- CBC with differential
- Complete Metabolic Panel (sodium, potassium, chloride, carbon dioxide, glucose, urea nitrogen, creatinine, calcium, total protein albumin, total bilirubin, alkaline phosphatase, AST, ALT)
- Serum Phosphorus
- Estimated creatinine clearance (Cockcroft-Gault Formula)

Medical history should include current or recent use of illicit drugs, alcohol, and tobacco; any prescription medications within the last 30 days; all diagnoses active within the preceding 30 days; past medical history; and current contraception method if participants are engaging in sexual activity.

The medication history should consist of the following: all prescription, nonprescription medications, alternative therapies, vitamins and dietary supplements taken within 30 days of entry, including actual or estimated start and stop dates. Following entry, all prescription and nonprescription medications taken since the last clinic visit should be recorded.

Weight will be measured and recorded on the source document at screening to calculate creatinine clearance at entry, at each dosing visit, and at the final safety visit. Height will be measured and recorded once at screening.

Blood pressure, temperature, and pulse rate will be collected at all visits and recorded on the source documents.

Complete physical examination is required at screening. The complete physical exam does not include genital, breast, and rectal examinations.

9.2.2 Day 1 (Visits 2 and 7) Genvoya Dosing Under Direct Observation followed by pharmacokinetic sampling.

Participants who satisfy the inclusion criteria will be asked to return to the DDU on Day 1. Individuals will be given a single oral dose of Genvoya whole tablet (Whole Tablet Period) or a crushed/dissolved Genvoya tablet mixed in water (crushed/dissolved Tablet Period) under direct observation. They will undergo pharmacokinetic sampling at the DDU for the components of Genvoya as outlined in **Table 2** (Pharmacokinetic sampling schedule) and **Table 3** (Schedule of Events). Approximately 8 mL will be collected at all pharmacokinetic time points. Serum creatinine will be collected once, pre-dose, for estimated creatinine clearance. Female participants will have a POCT qualitative urine pregnancy test prior to dosing and negative test results are required for participants to continue with dosing/the study visit. Any positive POCT qualitative urine pregnancy test results will be confirmed with a serum quantitative pregnancy test.

At entry, all signs, symptoms, and diagnoses within 30 days prior to entry will be recorded, including actual and estimated dates of onset and resolution. After entry, all new diagnoses,

signs and symptoms will be recorded at the visit they are reported and should include status, date of onsent, date of discovery and date of resolution, if applicable.

For the WholeTablet Period, subjects will be given a single oral dose of a whole Genvoya tablet under direct observation. Participants will be asked to return to the DDU approximately 7 days after receiving the whole tablet dose, in order to complete the first study safety evaluation. Participants will be required to undergo a minimum 14-day washout period following receipt of the Genvoya whole tablet.

For the Crushed/Dissolved Tablet Period, subjects will be given a single oral dose of a crushed/dissolved Genvoya tablet under direct observation. The solution of crushed/dissolved Genvoya tabled mixed in water will be prepared at the Johns Hopkins Investigational Drug Pharmacy. Participants will be asked to return to the DDU approximately 7 days after receiving the crushed/dissolved tablet dose, in order to complete the final study safety evaluation.

Table 3. Schedule of Events

Evaluations	¹Screening	Whole Tablet Period²					Safety Visit	Crushed/Dissolved Tablet Period²				Safety Visit
	Visit 1	Visit 2	Visit 3	Visit 4	Visit 5	Visit 6	Visit 7	Visit 8	Visit 9	Visit 10	Visit 11	
	Day -30	Day 1	Day 2	Day 3	Day 4	Day 8	Day 1	Day 2	Day 3	Day 4	Day 8	
Informed Consent	X											
Vital Signs (BP, HR, Temp)	X	X	X	X	X	X	X	X	X	X		
Weight	X	X					X				X	
Height	X											
HIV-1/2 Ag/Ab	X											
HBsAg	X											
CBC w/ Diff	X										X	
Complete Metabolic Panel	X	X²				X	X²				X	
Serum Phosphorus	X					X					X	
POCT Qualitative Urine HCG (female participants only)	X	X					X					
³Estimated Creatinine Clearance	X	X					X				X	
Medical /Medication History	X											
Physical Exam	X											
Adverse Event Assessment		X	X	X	X	X	X	X	X	X	X	
Concomitant Medications		X	X	X	X	X	X	X	X	X	X	
Targeted Physical Exam⁴		X	X	X	X	X	X	X	X	X	X	
Observed whole dose Genvoya		X										
Observed crushed/dissolved dose Genvoya							X					
Plasma Pharmacokinetics⁵		X	X	X	X		X	X	X	X		

¹Screening within 30 days of entry

²Serum creatinine only

³Creatinine Clearance estimated by Cockcroft-Gault formula

⁴A targeted physical exam will only be completed if clinically indicated

⁵Pharmacokinetic sampling time points pre-dose and 0.25, 0.5, 0.75, 1, 1.5, 2, 3, 4, 5, 6, 10, 14, 24, 48, and 72 hours after each dose. There is a +/- 5 min window for 0.25hr to 1.5hr PK specimen collection and a +/- 15 min window for 2hr to 14hr PK specimen collection. Windows for 24, 48 and 72 hr PK specimen collection outlined in section 9.2.3-9.2.5.

9.2.3 Day 2 (Visits 3 and 8) – 24 hour PK sampling

Participants will return to the clinic for a 24 ± 1 hour pharmacokinetic blood sample. They will be asked about any new or continuing adverse events and concomitant medications. A targeted physical examination will be performed if any adverse event is reported.

9.2.4 Day 3 (Visits 4 and 9) – 48 hour PK sampling

Participants will return to the clinic for a 48 ± 2 hours pharmacokinetic blood sample. They will be asked about any new or continuing adverse events and concomitant medications. A targeted physical examination will be performed if any adverse event is reported.

9.2.5 Day 4 (Visits 5 and 10) – 72 hour PK sampling

Participants will return to the clinic for a 72 ± 4 hours pharmacokinetic blood sample. They will be asked about any new or continuing adverse events and concomitant medications. A targeted physical examination will be performed if any adverse event is reported.

9.2.6 Day 8 (Visits 6 and 11) - Safety Visit

Subjects will return to the DDU 7 days ± 3 days following the direct observed dose of Genvoya for a safety study visit. Subjects will undergo clinical and laboratory evaluations as outlined in the schedule of events. A targeted physical examination is to be driven by any signs or symptoms previously identified that the subject has experienced since the last visit, or newly occurring that the subject has experienced since the previous visit. A targeted physical examination is not necessary if the subject does not have new symptoms. In the absence of new symptoms, a target physical examination may still be required to document resolution of previous findings on physical examination.

Study subjects will be reminded that they must not participate in a conception process. Participants will also be advised regarding HIV prevention during the study.

Adverse events will be monitored throughout the study according to the DAIDS Table for Grading the Severity of Adult and Pediatric Adverse Events. Participants experiencing grade ≥ 3 toxicity that is deemed by the investigator as associated with Genvoya will be discontinued from the study. These subjects will be followed until resolution, return to baseline values, stabilization, or an adequate explanation can be given for their condition. They will complete the last safety evaluation visit outlined in the schedule of events. Patients experiencing grades 1 or 2 toxicity will continue in the study at the discretion of the investigator.

At visit 6, participants will be scheduled to return to the DDU to start the Crushed/Dissolved Tablet Period of the study.

The final safety evaluation visit is also the premature study drug discontinuation visit. They will undergo clinical and laboratory assessments as outlined in the schedule of events.

9.2.7 Evaluations for Subjects Who Do Not Start Study Drugs

No follow up evaluations are required for study subjects who do not start study drugs.

9.2.8 Completion of Protocol

A subject is considered to have completed the study if he/she completed the two study periods for whole and crushed/dissolved Genvoya plasma pharmacokinetic sampling.

9.2.9 Study Drug Modifications

Dose modifications/reductions/interruptions of study medications to manage toxicity are not allowed in this study. Subjects requiring dose modifications/reductions/interruptions for the management of toxicities at any time during the study will be taken off study.

10 TOXICITY MANAGEMENT

Dose modifications/reductions/interruptions of study medications to manage toxicity are not allowed in this study. Subjects requiring dose modifications/reductions/interruptions for the management of toxicities at any time during the study will be taken off study and complete the safety evaluation. Adverse events will be graded according to the DAIDS Table for Grading the Severity of Adult and Pediatric Adverse Events.

- Grade 1 Toxicities

For all Grade 1 toxicities study participants may continue on study at the discretion of the study investigator and will be followed carefully.

- Grade 2 Toxicities

For all Grade 2 toxicities the participant may continue on study at the discretion of the site investigator.

- Grade ≥ 3 Toxicity

If a participant has a Grade 3 or greater toxicity attributed to the study drug, the participant will not receive any further Genvoya dosing. These individuals will be followed until resolution, stabilization, return to baseline values or an adequate explanation can be given for their condition. They will complete the evaluations scheduled for the safety visit. Additional clinic visits and evaluations might be necessary as medically indicated.

11 CRITERIA FOR DISCONTINUING FURTHER GENVOYA DOSING

- Requirement of concomitant medication that is judged by the site investigator to interfere with study continuation.
- Request by the subject to withdraw.
- Clinical reasons believed life threatening by the investigator, even if not addressed in the toxicity management of the protocol.
- Subject judged by the investigator to be at significant risk of failing to comply with the provisions of the protocol as to cause harm to self or seriously interfere with the validity of the study results.
- Drug toxicity as defined in Section 10.
- At the discretion of the investigator, regulatory agencies, or pharmaceutical sponsor.
- Failure by the subject to take study medications as instructed.
- Failure to complete a pharmacokinetic sampling visit within the allowable timeframe.

12 CRITERIA FOR PREMATURE STUDY DISCONTINUATION

- Request by the study subjects to withdraw.
- Drug toxicity as defined in Section 10.
- Request of the primary care provider if s/he is no longer in the best interest of the subject.
- Subject judged by the investigator to be at significant risk for failing to comply with the provisions of the protocol as to cause harm to self or seriously interfere with the validity of the study results.
- Imprisonment or the compulsory detention for treatment of either psychiatric or physical illness.
- At the discretion of the investigator, regulatory agencies, or pharmaceutical sponsor.
- Toxicities as outlined in Section 10 of the protocol.

13 STATISTICAL CONSIDERATIONS

An equivalence approach with no-effect boundaries of 80 to 125% will be employed, in accordance with the FDA guidance on bioequivalence studies, which define bioequivalence as “the absence of a significant difference in the rate and extent to which the active moiety becomes available at the site of action when administered at the same molar dose under similar conditions (11).

In order to test the primary hypothesis, log-transformed $AUC_{0-\infty}$ and C_{max} after a single dose for crushed/dissolved

Table 4

Confidence Level	Sample Size (N)	Target Distance from Mean to Limits	Actual Distance from Mean to Limits	Standard Deviation (\$)
0.900	5	0.050	0.048	0.050
0.900	13	0.050	0.049	0.100
0.900	27	0.050	0.049	0.150
0.900	46	0.050	0.050	0.200
0.900	70	0.050	0.050	0.250
0.900	3	0.100	0.084	0.050
0.900	5	0.100	0.095	0.100
0.900	9	0.100	0.093	0.150
0.900	13	0.100	0.099	0.200
0.900	19	0.100	0.099	0.250
0.900	3	0.150	0.084	0.050
0.900	4	0.150	0.118	0.100
0.900	5	0.150	0.143	0.150
0.900	7	0.150	0.147	0.200
0.900	10	0.150	0.145	0.250
0.900	3	0.200	0.084	0.050
0.900	3	0.200	0.169	0.100
0.900	4	0.200	0.177	0.150
0.900	5	0.200	0.191	0.200
0.900	7	0.200	0.184	0.250
0.900	2	0.250	0.223	0.050
0.900	3	0.250	0.169	0.100
0.900	4	0.250	0.177	0.150
0.900	4	0.250	0.235	0.200
0.900	5	0.250	0.238	0.250

versus whole tablets will be compared. The adjusted mean differences will be estimated and their 90% confidence intervals calculated. In the case of $AUC_{0-\infty}$ and C_{max} , the estimated differences and confidence limits will be exponentiated in order to compare ratios between tablet forms.

Statistical Methods

The sample size was calculated according to the formulas for a multiplicative model (12). **Table 4** includes sample size calculations for this proposed study (13). If the mean C_{max} ratio or AUC ratio is 1, a sample size of 5 subjects produces a two-sided 90% confidence interval (0.952, 1.048) (i.e., a distance from the mean to the limits that is equal to 0.048, when the estimated standard deviation is 0.050). A sample size of 10 subjects produces a two-sided 90% confidence interval (0.855, 1.145) if the mean C_{max} ratio or AUC ratio is 1, and the estimated standard deviation is 0.25. Assuming a dropout rate of 10%, a sample size of 12 subjects will be required to provide 90% power to demonstrate the bioequivalence of C_{max} with 90% confidence intervals (CI) of 80% and 125%.

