Johns Hopkins Hospital
[name]
[name]
[contact]
[contact]
Email: [contact]

Study Coordinators

[name], MPH, CCRP
Division of Clinical Pharmacology
[name]
[name]
[contact]
[contact]
Email: [contact]

[name]
Division of Clinical Pharmacology
[name]
[name]
[contact]
[contact]
Email: [contact]

SCHEMA

Rationale	Genvoya, a once-daily single fixed-dose combination tablet for treatment of HIV-infection, consists of two nucleoside reverse transcriptase inhibitors (NRTIs), emtricitabine (FTC) and tenofovir (TFV) alafenamide fumarate (TAF), the integrase strand transfer inhibitor (InSTI) elvitegravir (EVG), and the boosting agent cobicistat (COBI). It is unknown whether Genvoya, taken as a crushed/dissolved tablet, is bioequivalent to when taken as a whole tablet. This is crucial information since a substantial number of HIV-infected individuals suffer from pill aversion that could lead to non-adherence and treatment failure.
Design	Within-subject, fixed-order, two-period, open label study to determine the bioequivalence of oral single dose of whole and crushed/dissolved tablets of Genvoya in healthy adult male and female research participants administered under direct observation.
Population	Up to 20 adult male and female healthy research participants will be enrolled to complete 12.
Intervention	Whole Tablet Period: Single observed oral dose of Genvoya whole tablet Crushed/dissolved Tablet Period: Single observed oral dose of Genvoya crushed/dissolved tablet
Outcome Measures	Primary: To investigate the bioequivalence of oral single whole tablet and crushed/dissolved tablet of Genvoya by characterizing the plasma $AUC_{0-\infty}$ and C_{max} of EVG, COBI, FTA, TAF, and TFV in plasma, after single doses of whole tablet and crushed/dissolved tablet in healthy male and female adult research participants. Secondary: To compare other pharmacokinetic parameters of oral single whole tablet and crushed/dissolved tablet of Genvoya by characterizing the plasma T_{max} and terminal elimination half-life of EVG, COBI, FTA, TAF, and TFV after single doses of whole tablet and crushed/dissolved tablet in healthy male and female adult research participant.

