13.2 Accrual

The team expects to accrue 2-3 subjects per month. Expected time to reach full accrual of 12 evaluable participants, is 6-9 months.

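### The 90% power claim is not met in the plan's own worked case: at SD 0.25 and a true ratio of 1, power is about 66% with 10 subjects and 79% with 12.

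*Combined protocol and SAP*

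**What the plan says.** The design is described in the Schema as a "Within-subject, fixed-order, two-period, open label study". Section 13 sets the criterion: "An equivalence approach with no-effect boundaries of 80 to 125% will be employed". AUC and Cmax are log-transformed; "The adjusted mean differences will be estimated and their 90% confidence intervals calculated", and "the estimated differences and confidence limits will be exponentiated in order to compare ratios between tablet forms".

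The sample size rests on Table 4, which lists a confidence level of 0.900, N, the distance from the mean to the limits, and an SD. The text says a multiplicative model was used and gives two examples at a ratio of 1. The first is 5 subjects with SD 0.05, interval (0.952, 1.048). The second has SD 0.25: "A sample size of 10 subjects produces a two-sided 90% confidence interval (0.855, 1.145"). The next sentence is the power claim: "Assuming a dropout rate of 10%, a sample size of 12 subjects will be required to provide 90% power to demonstrate the bioequivalence" of Cmax. It gives neither an SD nor a true ratio.

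On what 12 counts, the Schema says: "Up to 20 adult male and female healthy research participants will be enrolled to complete 12". Section 6 has the same intent, and Section 13.2 speaks of "Expected time to reach full accrual of 12 evaluable participants".

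**The concern.** A confidence-interval half-width is not a power. Table 4 shows that if the observed ratio were 1 and the observed SD 0.25, an interval from 10 subjects would fit inside 80–125%. It does not give the probability that the interval fits once the observed ratio and observed SD vary from sample to sample. The text moves from the first statement to the second, and a 90% confidence level becomes 90% power.

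This sentence is the plan's only statement of power. If it is taken at face value, a comparison that fails the 80–125% criterion looks like a result from a study with a 10% chance of missing true equivalence. At the SD of the worked case that chance is 21% with 12 completers and 34% with 10, for each comparison.

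Two smaller problems sit in the same paragraph. Twelve is reached there by inflating for dropout, whereas elsewhere it is the number who complete. And the example intervals are additive around 1, although the model is said to be multiplicative and the analysis is on the log scale.

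**Working it through.** **Inputs.** From Section 13: limits 0.80 and 1.25, which are ±ln 1.25 = ±0.2231 on the log scale; a two-sided 90% interval, equivalent to two one-sided tests at 0.05 each; true ratio 1 and SD 0.25 from the 10-subject example; dropout 10%. From the Schema: a paired design, so one log difference per subject and n − 1 degrees of freedom.

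**1. The plan's own figures.** Half-width = t(0.95, n − 1) × SD / √n.

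- n = 5, SD 0.05: 2.132 × 0.05 / √5 = 0.0477 (Table 4: 0.048).
- n = 10, SD 0.25: 1.833 × 0.25 / √10 = 0.1449 (Table 4: 0.145).

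All 25 rows of Table 4 reproduce to rounding with this formula. The SD is therefore that of the within-subject difference, and the table holds precision only.

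**2. From 10 to 12.** 10 / (1 − 0.10) = 11.1, rounded up to 12. In Table 4, N = 10 occurs only with SD 0.25.

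**3. Power of the planned test.** Let d be the mean log difference and s its sample SD. The comparison passes when d − t·s/√n > −0.2231 and d + t·s/√n < 0.2231. Power is the probability of both, with d normal (SD 0.25/√n), integrated over the chi-square distribution of s².

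| Completers | Ratio 1, SD 0.25 | Ratio 0.95, SD 0.25 | Ratio 1, SD 0.20 | Largest SD giving 90% at ratio 1 |
|---|---|---|---|---|
| 10 | 66.3% | 58.2% | 89.1% | 0.197 |
| 11 | 73.2% | 64.2% | 92.7% | 0.209 |
| 12 | 78.8% | 69.3% | 95.1% | 0.220 |

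Simulation with 300,000 trials per n at SD 0.25 and ratio 1 gave 66.2%, 73.2% and 78.8%. At SD 0.25 and ratio 1, n = 15 gives 89.9% and n = 16 gives 92.1%, so 90% needs 16 completers.

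**4. Can another reading recover 90%?** At SD 0.25, for n = 10 and n = 12:

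- normal approximation: 76.1% and 85.2%;
- raw-scale limits 0.80–1.25: 65.3% and 77.4%;
- symmetric raw margin ±0.25: 79.5% and 88.9%;
- 0.25 read as a CV of the difference: 68.2% and 80.4%.

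About 90% appears only with a test that is not planned. A single one-sided t-test gives 89.8% at n = 10 (raw margin 0.25) and 89.4% at n = 12 (log scale). A single one-sided normal approximation gives 92.6% at n = 12, and alpha 0.10 per side gives 90.9% at n = 12.

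**5. Example intervals on the log scale.** exp(±0.0477) = (0.953, 1.049) and exp(±0.1449) = (0.865, 1.156), against the printed (0.952, 1.048) and (0.855, 1.145).

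**6. Is SD 0.25 pessimistic? (Illustration only.)** Table 2 gives between-subject means and SDs. Log SD = √ln(1 + CV²); SD of the difference = log SD × √(2(1 − ρ)), where ρ, the within-subject correlation, is assumed because the plan does not give it. For Cmax with 12 completers and ratio 1:

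| Analyte | CV | Power, ρ = 0.7 | ρ = 0.8 | ρ = 0.9 |
|---|---|---|---|---|
| EVG | 0.4/1.7 = 24% | 98% | >99% | >99% |
| FTC | 0.5/1.9 = 26% | 95% | 99% | >99% |
| COBI | 0.4/1.1 = 36% | 69% | 89% | >99% |
| TAF | 0.08/0.16 = 50% | 29% | 57% | 92% |

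For TAF Cmax, an SD of 0.25 or less needs ρ of at least 1 − (0.25/0.472)²/2 = 0.86. No SD is tabulated for TFV.

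**The case against.** The strongest objection is that the power sentence names no SD. The 0.25 is borrowed from the example before it and is the largest value in Table 4. At SD 0.20, also in the table, power is 89% with 10 subjects and 95% with 12. This stands as a caveat on how the SD was identified. It does not rescue the claim: N = 10 is paired only with SD 0.25, that example comes immediately before the claim, and no passage links SD 0.20 to 10 or 12 subjects. On either reading, the 90% lacks the inputs needed to check it.

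Second, the operative plan is 12 completers with up to 20 enrolled, so 79% describes the intended study better than 66%. That is fair. The 66% belongs to the 10 evaluable subjects implied by the dropout arithmetic.

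Third, the dropout clause is an inconsistency in what 12 means rather than a wrong figure, and the shift in the example intervals (about 0.01 per limit at most) changes no conclusion. Both are true; they are corrections to make in the same edit.

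Fourth, Section 13 also offers precision as a justification, and those half-widths are right. They stand as precision statements. Finally, Table 2 describes HIV-infected adults and the correlation is assumed, so step 6 is only illustrative; for EVG and FTC Cmax it gives at least 95% power across the correlations shown.

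**Conclusion.** The concern holds. Table 4 contains no power calculation, and the stated 90% is not met at the SD of 0.25 used in the worked case that leads to 12. With the planned paired log-scale test and a true ratio of 1, power per comparison is 79% with 12 completers and 66% with the 10 subjects behind the calculation. At a ratio of 0.95 these fall to 69% and 58%. The claim would be right for an SD up to about 0.22 with 12 completers, or about 0.20 with 10, but the plan states no such assumption.

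The result assumes normally distributed log differences and reads the Table 4 SD as that of the within-subject difference, which reproduction of the table confirms. It concerns one comparison; the primary objective covers Cmax and AUC for five analytes, and the probability that all pass cannot exceed that of the weakest one.

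**What to change.** Keep the trial size and replace the power sentence in Section 13 with figures that can be checked, for example: *With 12 completers, an SD of the within-subject log ratio of 0.25 and a true ratio of 1, the power for one 90% confidence interval to lie within 80–125% is 79% (69% at a true ratio of 0.95); 90% power requires an SD of at most 0.22.* If the authors had a smaller SD in mind, they should state it, give its source and quote the power that follows.

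In the same edit:

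- define 12 as the number of completers, in line with the Schema, Section 6 and Section 13.2, and remove the 10% dropout clause from the power statement;
- restate the example intervals as (0.953, 1.049) for n = 5, SD 0.05, and (0.865, 1.156) for n = 10, SD 0.25;
- label Table 4 as a precision table.

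The cost is a wording change in Section 13. No participants, visits or analyses are added; the declared power becomes less favourable.
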